## 3.2 Endpoints

#### 3.2.1 Primary endpoints

- Number of Adverse events (AEs), serious AEs (SAEs) (Common Terminology Criteria Adverse Events [CTC-AE]) from ICF signature to D29, including target knee pain and tenderness, erythema, swelling, local pain at injection site.
- Vital signs from D-7 to D8, ECG from D-7 to D1: Mean change, number of Potentially Clinically Significant Abnormality (PCSA), Percentage of participants with PCSA
- Laboratory changes (Red Blood Cells (RBC), White Blood Cells (WBC), Hemoglobin (Hb), platelets, alanine transaminase (ALT), aspartate transaminase (AST), glycemia, amylasemia, creatinin clearance) from D-7 to D8: Mean changes number of PCSA, Percentage of participants with PCSA.

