## Recruitment of participants

Participants will be recruited via investigators' patient registry or via advertising. More information is provided in Patient Recruitment Procedure.

A Screening visit at D-7 (D-14 to D-4) will be performed at study site and if the participant still agrees to participate in the study after the investigator has answered all his/her questions, the participant will sign the informed consent form. This visit should take place around 7 days before the randomization day (D-14 to D-4). During this visit, the eligibility of the participant will be evaluated.

The Randomization visit (Day 1 to Day 2) will be performed at study site and the participant will be randomized in the study after review of inclusion & exclusion criteria. The participant will be hospitalized for 24 hours. The IMP IA injection will be performed by the investigator after a veinous infusion line has been set up (see Investigator & Pharmacy manuals and sections 1.2 and 6.2.2). Participant will be monitored during the 24-hour hospitalization and will be discharge on D2.

The Follow-up visit at D4 (±1 day) will be a virtual visit by phone call unless abnormal, clinically significant findings are observed upon discharge or at the investigator's discretion (participants should then be brought back to the clinic for re-evaluation).

The Follow-up visit at D8 ( $\pm 2$  days) will be a face-to-face visit. Participant will be asked to fill in a diary and a NRS questionnaire up to Day 29 to record any AE (in particular pain in the target knee) and analgesic medication taken.

The End of Study (EoS) visit at D29 (±2 days) will be a virtual visit by phone call unless abnormal, clinically significant findings are observed upon discharge or at the investigator's discretion (participants should then be brought back to the clinic for re-evaluation). Participant will be asked to send back to the Investigator the diary and the NRS questionnaire

An independent Data and Safety Monitoring Board (DSMB) will be set up for this study (see DSMB Charter) and will review safety data during the study. The DSMB will be composed of 2 physicians specialized, one in rheumatology and one in diabetology.

Members will review the safety data in sessions on a regular basis during the study, and at any time if any SAE at least possibly related to liraglutide or safety issue occurs (see section 11.1.5 and DSMB Charter).

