## Stopping rules

The study will be immediately suspended, and no additional IMP administered pending review and discussion of all appropriate study data by the DSMB if 1 or more participants develop any of the following adverse events deemed to be possibly, probably, or definitely related to the IMP by the Investigator and/or Medical Monitor, based upon close temporal relationship or other factors:

- Severe local reaction within 7 days after injection
- Clinical manifestations of hypoglycemia
- Severe gastro-intestinal adverse event
- Potentially clinically significant ECG abnormalities.
- Any serious adverse event considered reasonably related to the IMP (SAR) by the Principal Investigator.

The study will not be restarted until all parties have agreed to the course of action to be taken and the EC has been notified.

Dose limiting toxicity (DLT) describes side effects of a drug that are serious enough to prevent an increase in dose or level of that treatment.

When more than 1 DLT occurs in a dosing cohort, dose escalation must be stopped and this dose level will be identified as the non-tolerated dose.

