#### 8.1.1 Physical examination

A physical examination will be conducted at screening, D1, D2 and D8 visits. A symptom-based physical examination will include organ systems, which are deemed, at the discretion of the Investigator, necessary to be evaluated.

Height (at screening only) and weight will also be measured at screening, D1 and D8 and recorded (Body mass index will be calculated automatically).

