#### 8.1.5 Local safety

The evaluation of IA injection site reaction following IMP administration will be performed by the Investigator or designees as outlined in section 1.2.2. Findings at the site of injection such as, but not limited to tenderness, erythema, and swelling, will be recorded in the eCRF in 3 different grades (mild/moderate/severe).

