#### 8.5.3 Hospital discharge, D2

Before participant discharge from the hospital, the investigator or delegate will

- perform a physical exam and record vital signs,
- remind the participant
  - o to assess target knee pain [NRS] (based on the previous 24 hours) on a daily basis from D3 to the next visit date (D8),

- o to fill in the diary from D2 (after hospital discharge) up to the next visit (D8) to self-report adverse events and pain killer medication,
- give appointment for a virtual visit (phone call) at D4 ± 1d and for a face-to-face visit on D8 ± 2 days.

No specific physical limitation is recommended from the day after the injection.

In case of safety concerns after hospital discharge, the participant will be asked to call the investigator / to return to the hospital for an unscheduled safety control visit according to the investigator judgement.

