#### 8.5.6 EoS visit: Phone call (Virtual visit), D29 ± 2d

The Investigator or delegate call the participant by phone and will ensure that the participant completed the diary (AE, target knee pain, pain killer intake, concomitant medications) and will remind the participant to send the diary and the NRS questionnaire as planned.

The investigator will also inquire for any ongoing AEs or SAEs, worsening of AEs or SAEs, or development of new AEs or SAEs.

In case of safety concerns, the participant will be asked to return to the hospital for a safety control visit.

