#### 11.3.4 Recording and follow-up of AE and/or SAE

### AE and SAE recording

When an AE/SAE occurs, either spontaneously revealed by the patient or observed by the Investigator, and whether believed by the Investigator to be related or unrelated to the study drug, it is the responsibility of the Investigator to review all documentation (e.g., hospital progress notes, laboratory, and diagnostics reports) related to the event.

- The Investigator will record all relevant AE/SAE information on the AE CRFs/worksheets at each examination.
- It is not acceptable for the Investigator to send photocopies of the participant's medical records to the Sponsor in lieu of completion of the AE eCRF page.

- There may be instances when copies of medical records for certain cases are requested by the Sponsor. In this case, all participant identifiers, with the exception of the participant number, will be blinded on the copies of the medical records before submission to the Sponsor.
- The investigator will attempt to establish a diagnosis of the event based on signs, symptoms, and/or other clinical information. In such cases, the diagnosis (not the individual signs/symptoms) will be documented as the AE/SAE.
- As far as possible, each AE/SAE is described by: duration (start and end dates), event verbatim, solicited/unsolicited, frequency (relationship to the study treatment), intensity grade, seriousness, action taken and outcome.

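### SAP 12.2.5 does not deliver the local tolerability analysis in protocol 10.1.4: Table 3.3 is introduced as severe-only, nothing is shown over time, and the graded local record has no clearly assigned table or listing

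*Protocol*

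**What the plan says.** Endpoint. Protocol 3.2.1 counts adverse events from consent to D29, "including target knee pain and tenderness, erythema, swelling, local pain at injection site".

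Collection. Protocol 8.1.5 sets up a structured record of the injection site in three grades: "The evaluation of IA injection site reaction following IMP administration will be performed by the Investigator or designees as outlined in section 1.2.2". Flowchart 1.2.2 marks the local reaction row at 1, 2, 3, 4, 5 and 24 h. The whole-study flowchart 1.2.1 marks it on D1 and D2 only.

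Planned analysis. Protocol 10.1.4 (Local tolerability) specifies two outputs: participants with injection-site reactions, overall and by maximum severity per treatment group; and the incidence over time of adverse events tied to local findings. The opening of 10.1.4 also commits to listing every item of safety data.

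SAP. Section 12.2.5 has one introductory sentence and one table shell, numbered 3.3 in SAP 17. The sentence says the table presents adverse event details for severe injection-site reactions. The shell crosses kind of reaction with maximum toxicity grade by arm, with rows for any grade, mild, moderate and onward. It has no time axis and no statement of data source. SAP 18 names 20 listings for the clinical study report.

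**The concern.** Local tolerability is a main new question here. Protocol 2.3 acknowledges that safety after intra-articular injection has not been studied in humans, and the local signs are named in the primary endpoint. The protocol collects a dedicated graded record and says how local findings will be summarised. The SAP should turn that into outputs.

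As written, it does so only in part. Taken literally, the introductory sentence would drop mild and moderate reactions from the one table meant for them. A summary specified in the protocol would not be produced. A reader of the report could not see when reactions appeared, or whether a count came from the scheduled examinations or from adverse event reports.

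**Working it through.** The plan states no figure on this point, so the check sets the protocol against the SAP and then counts what is affected.

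**1. Protocol against SAP**

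| Protocol 10.1.4 | SAP | Match? |
|---|---|---|
| Reactions overall and by maximum severity | Table 3.3 shell has any-grade, mild and moderate rows, but the sentence above it restricts it to severe reactions | Shell yes, sentence no |
| Incidence of local adverse events over time | No table in SAP 17; Table 3.3 has no time dimension | No |
| All safety data listed | No listing in SAP 18 is titled for the graded local record | Not shown |

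**2. Effect of the word severe.** Suppose only participants with a severe reaction enter Table 3.3. Their maximum grade is then severe or worse, so the mild and moderate rows of the any-kind block are zero by construction. The sentence and the shell cannot both be right.

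**3. Source of Table 3.3.** The SAP allows three readings:

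- *Adverse event records.* The graded form from 8.1.5 then has no table at all.
- *The graded form.* Table 3.3 then stops at 24 h and omits local adverse events reported after discharge.
- *Both.* The table then mixes scheduled examinations with reported events, with no split.

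The by-time summary is missing under every reading.

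**4. Size of the graded record**

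- Scheduled gradings per participant: 1, 2, 3, 4, 5 and 24 h = 6.
- Participants: four cohorts of 8, plus the ninth participant in cohort 3 (SAP 9.3): 8 + 8 + 9 + 8 = 33.
- Graded assessments if all are done: 6 × 33 = 198. With the planned 32 participants: 6 × 32 = 192.
- Listings in SAP 18: 16.2.1 to 16.2.20 = 20. Titled for local reactions: 0.

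**5. Comparison within the SAP.** Knee pain gets three tables by timepoint (4.1 to 4.3). Vital signs and glycemia are also tabulated over time. The local signs, graded six times in 24 h, are not.

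**The case against.** The best defence is that the source can be inferred. The introductory sentence speaks of adverse event details, the table sits within section 12.2, and its grade labels match those of the treatment-emergent tables. Local adverse events of every grade with onset in the treatment period would also appear in Tables 3.1.1 to 3.1.3. Each event is recorded with "duration (start and end dates), event verbatim, solicited/unsolicited", so timing could be rebuilt from Listing 16.2.9. Listing 16.2.7, on the injection, might carry the graded record. Protocol 10.1.4 also confines summarised treatment-emergent events to a 7-day window, which gives some guidance on late onsets.

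Much of this is fair. It means that mild and moderate local adverse events would not vanish from the report. But if Table 3.3 rests on adverse event records, the graded form has no table; the content of Listing 16.2.7 is not given; and rebuilding timing by hand is not the summary the protocol specifies. Nothing here explains the word severe.

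A reader might infer more: that because structured grading ends at 24 h, later mild or moderate tenderness, erythema or swelling goes unrecorded, or that the suspension rule for "Severe local reaction within 7 days after injection" is unsupported. The documents do not bear this out:

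- Adverse events are collected to the end of study (8.2.1), graded by the investigator (8.2, 11.3.4), followed at later contacts (8.2.3), and re-recorded when the grade changes (11.3.4).
- Severe site reactions are events of special interest (8.2.6).
- The diary runs to D29, and knee pain is rated daily to D8 and then weekly.
- For significant findings at discharge, or at the investigator's discretion, the D4 and D29 calls become visits: "participants should then be brought back to the clinic for re-evaluation". After discharge, a safety concern can lead the participant "to return to the hospital for an unscheduled safety control visit".
- At D29, "The investigator will also inquire for any ongoing AEs or SAEs, worsening of AEs or SAEs, or development of new AEs or SAEs".
- D8 is face to face, with an examination, though a discretionary one: "A symptom-based physical examination will include organ systems, which are deemed, at the discretion of the Investigator, necessary to be evaluated".

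The solicited/unsolicited field also suggests that some events are prompted for. The diary form and the Investigator manual are not among the documents, so whether local signs are prompted cannot be settled. The dog data in protocol 2.3, with no liraglutide left in the joint after 24 h, make an early-weighted schedule defensible.

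**Conclusion.** SAP 12.2.5 is wrong as written because it is inconsistent with protocol 10.1.4. The severity is minor. Three parts rest on the text alone: the severe-only sentence contradicts the all-grade shell and the protocol; the by-time summary has no table; and no listing is titled for a record of up to 198 graded assessments. The count assumes a full cohort 4 of eight and no replacements beyond the ninth participant in cohort 3.

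Two things remain open: whether a programmer would apply the word severe literally, and whether an existing listing would carry the graded record. The defect concerns how one component of the primary endpoint is reported. It does not show that reactions were missed, and the documents give no basis for estimating under-recording.

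The 24 h end of structured grading is a limitation to state, not an error. Adding checks after cohort 3 would reach at most 8 of 33 participants (24%), or none if cohort 4 is complete, and would make ascertainment uneven across doses and within pooled placebo.

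**What to change.** In the SAP, before database lock:

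1. Delete the word severe from the sentence introducing Table 3.3.
2. State whether Table 3.3 uses the graded local-reaction form, local adverse events, or both, and that all grades are included.
3. Add a by-time summary: each of the six D1-D2 timepoints for the form; and, for local adverse events, onset up to 24 h, after 24 h to day 7, and after day 7. Define the day-7 cut, because protocol 10.1.4 counts the dosing day as day 1 while SAP 9.4 runs to 7 days after the injection date.
4. Add a listing of the graded local-reaction record to SAP 18.
5. Footnote Table 3.3 and the by-time summary: structured grading was scheduled only to 24 h, so later findings come from adverse event reporting.

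The cost is one edited sentence, one source statement, one summary, one listing and one footnote. It needs no new data, visit or protocol change. If the SAP is already final, produce these as protocol-specified outputs and record the change in the study report.

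For a future intra-articular study, consider repeating the three-grade form at D8 and asking a targeted question on tenderness, erythema and swelling at the D4 call. No such change is proposed for this trial.

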## 8.1.6 Target knee pain

The participants will also assess target knee pain using a numerical rating scale (NRS), 11 points (0-10) to assess pain of the target knee as outlined in section 1.2:

- At screening (as a mean of the previous 2 days)
- At D1: T0-4h as a mean of the previous 2 days and currently and every hour after T0 up to T0+6h
- At D2 before hospital discharge: assessment from IA injection to hospital discharge
- From D3 to D8 Visit: daily, assessment from the previous 24 hours
- From D15 to D29: weekly assessment based on pain during the previous 2 days.

A pre-paid and pre-printed envelope will be given to the participant on D8 visit for mailing these records to the Investigator.

## 8.2 Adverse events and serious adverse events

All AEs will be coded and graded according to the Division of AIDS, table for grading the severity of Adult and Pediatric Adverse Events (DAIDS, Corrected Version 2.1 July 2017).

The Investigator and any qualified designees are responsible for detecting, documenting, and recording events that meet the definition of an AE or SAE and remain responsible for following up AEs that are serious, considered related to the IMP or study procedures, or that caused the participant to discontinue the study.

The definitions of an AE, SAE and suspected unexpected serious adverse reactions (SUSAR), as well as the method of recording, evaluating, and assessing causality of AE and SAE and the procedures

for completing and transmitting AE, SAE, SUSAR and other reportable safety event reports can be found in Appendix 3.

The investigator and any designees are responsible for detecting, documenting, and reporting events that meet the definition of an AE or SAE as well as other reportable safety events.

Investigators remain responsible for following up AEs, SAEs, and other reportable safety events for outcome according to Section 8.2.3.

The investigator, who is a qualified physician, will assess events that meet the definition of an AE or SAE as well as other reportable safety events with respect to seriousness, intensity/toxicity and causality.

#### 8.2.1 Time period and frequency for collecting AE, AESI and SAE

All AEs and SAEs will be collected from the signing of the ICF until the end of study at the time points specified in the study flowcharts (section 1.2).

All SAEs will be recorded and reported to the Sponsor or designee immediately and under no circumstance should this exceed 24 hours of learning event, as indicated in section 11.3.

The Investigator will submit any updated SAE data to the Sponsor or designee within 24 hours of it being available.

#### 8.2.2 Method of detecting AEs and SAEs

The method of recording, evaluating, and assessing causality of AEs and SAEs and the procedures for completing and transmitting SAE reports are provided in section 11.3.

#### 8.2.3 Follow-up of AEs and SAEs

After the initial AE/SAE report, the Investigator is required to proactively follow each participant at subsequent visits/contacts. At the prespecified study end date, all SAEs will be followed until resolution, stabilization, the event is otherwise explained, or the participant is lost to follow-up. Further information on follow-up procedures is provided in section 11.3.

#### 8.2.4 Regulatory reporting requirements for SAEs

- Prompt notification by the Investigator to the Sponsor or designee of a SAE is essential so that legal obligations and ethical responsibilities towards the safety of participants and the safety of a study intervention under clinical investigation are met.
- The Sponsor has a legal responsibility to notify both the local regulatory authority and other regulatory agencies about the safety of a study intervention under clinical investigation. The Sponsor will comply with country-specific regulatory requirements relating to safety reporting to the regulatory authority, Independent Ethics Committees (IEC), and Investigators.
- Adverse events that are considered expected will be specified in the reference safety information (see IB).
- SUSARs are reported to regulatory authorities, Investigators, and IECs as follows:
  - For SUSARs that are life-threatening or result in death, reporting is no later than 7 days after first knowledge by the Sponsor, with all relevant follow-up information subsequently reported within an additional 8 days.

- o For SUSARs, other than those that are life-threatening or result in death, reporting is no later than 15 days after first knowledge by the Sponsor.
- An Investigator who receives an Investigator safety report describing a SAE, SUSAR, or any other specific safety information (e.g., summary or listing of SAEs) from the Sponsor will review and then file it along with the IB and will notify the IEC, if appropriate according to local requirements. It is the responsibility of the Sponsor to assess whether an event meets the criteria for a SUSAR, and therefore, is expedited to regulatory authorities.

#### 8.2.5 Pregnancy

If a pregnancy is reported, the Investigator should inform the Sponsor or designee within 24 hours of learning of the pregnancy and should follow the procedures outlined in section 11.4.

Abnormal pregnancy outcomes (e.g., spontaneous abortion, fetal death, stillbirth, congenital anomalies, ectopic pregnancy) are considered SAEs.

## 8.2.6 Adverse event of special interest (AESI)

An AESI is an AE (serious or nonserious) of scientific and medical concern specific to the Sponsor's product or program, for which ongoing monitoring and immediate notification by the Investigator to the Sponsor or designee is required.

All reported AESIs will be reviewed by an independent DSMB.

For AESIs, the Sponsor is to be informed immediately (i.e., within 24 hours), as per SAE notification guidelines described in section 11.3, even if a seriousness criterion is not met, using the corresponding pages of the case report form (to be sent) or screens in the eCRF:

- Pregnancy of a female participant entered in a study as well as pregnancy occurring in a female partner of a male participant entered in a study with IMP. It will be qualified as an SAE only if it fulfills one of the seriousness criteria (see section 11.3). Follow-up of the pregnancy in a female participant or in a female partner of a male participant is mandatory until the outcome has been determined (see section 11.4).
- Symptomatic overdose (serious or non-serious) with IMP. Any adverse event(s) associated with ("results from") an overdose of IMP will be reported as a serious adverse event, even if no other seriousness criteria are met.

Other project specific AESI:

- Anaphylaxis,
- Severe IMP injection site reactions (severe tenderness, erythema, swelling...),
- Hypoglycemia,
- Severe Gastro-intestinal disorder.

